#### 4.1.4.2 Temozolomide (TMZ): Regimen M

TMZ will be administered as follows:

During RT: Temozolomide will be administered orally at a dose of 75 mg/m^2 daily for 42 days concomitant with focal radiotherapy.

During the maintenance phase, four weeks after completing the RT, TMZ will be administered on day 1-5 of each cycle for up to 6 cycles:

- Dose in Cycle 1 will be 150 mg/m^2
- At the start of Cycle 2, if 150 mg/m^2 of TMZ was well tolerated in Cycle 1, the dose will be escalated to 200 mg/m^2

If the dose was not escalated at Cycle 2, escalation should not be done in subsequent cycles. Once escalated, the dose remains at 200 mg/m^2 per day for the first 5 days of each subsequent cycle.

TMZ dosage calculation is based on body surface area. For suggested capsule combinations on a daily dose please refer to the manufacturer guidelines. The dose should be rounded to the nearest 5 mg.

Patients should swallow TMZ capsules with a glass of water (~250 mL). TMZ capsules should not be chewed. To reduce nausea and vomiting, TMZ capsules should be taken on empty stomach. TMZ should be taken each day at the same time and this should be in the morning together with BIBW 2992.

Bedtime administration may be advised if not tolerated in the morning due to nausea, TMZ should then be taken at the same time each day to ensure a dose interval of approximately 24 hours and this should be in the evening approximately two hours after food intake to reduce nausea and vomiting.

Antiemetic therapy may be administered prior to and/or following administration of TMZ capsules.

Missed doses of TMZ can be made up if taken within 3 hours of the regularly scheduled time. Otherwise, the dose should be skipped and subjects should take the next scheduled dose at the usual time. Patients with emesis should not take a replacement dose.

TMZ re-treatment criteria:

Patients who show clinical benefit from treatment with the combination of BIBW 2992/TMZ may continue to receive treatment courses following the concomitant radiochemotherapy phase after a 4 weeks TMZ break for up to 6 cycles. Re-treatment criteria described in the package insert for Temodal® should be followed. In addition the following criteria should applied:

- $AST \leq 2.5 \times$  upper limit of institutional norm
- $Creatinine \leq 1.5 \times$  upper limit of institutional norm
- $Total\ bilirubin \leq 1.5 \times$  upper limit of institutional norm
- resolution of rash  $\geq$  Grade 3 or diarrhoea  $\geq$  Grade 3 to Grade 2 or less
- resolution of any other Grade 3 or greater drug-related adverse reaction (either related to BIBW 2992 or to TMZ) to Grade 1 or baseline (whichever is higher).

If a patient develops side effect due to TMZ, recommendation for dose reduction and dose interruption should be followed as per the most up to date Summary of Product Characteristic (SPC) recommendation of the manufacturer.

#### **4.1.5 Blinding**

Not applicable, open-label.

#### **4.1.6 Packaging, labelling, and re-supply**

BIBW 2992 will be supplied as film-coated tablets, supplied in, child-resistant, tamper-evident bottles. Bottles will be labelled with Study number (1200.38), medication number, product name, tablet strength, contents of bottle, storage information, use-by date, batch number, instruction for use, sponsor name and address. "For clinical trial use only" and "keep out of reach of children" will be printed on each label.

BIBW 2992 available dosage strengths will be 20 mg, 30 mg and 40 mg.

Each bottle contains 30 film-coated tablets of identical dosage strength. Single panel labels will be used. Examples of the bottle labels can be found in the investigator site file.

TMZ available dosage strength will be 5, 20, 100, 140 and 180 mg. TMZ capsules packaged will be in 5 ct (180 mg, 140 mg, 100 mg) or 20 ct (20 mg, 5 mg) amber glass bottles.

Drug accountability for BIBW 2992, and TMZ will be handled as outlined in Section 8.2.1. Re-supply for BIBW 2992 and TMZ will be actively managed by the sponsor according to the site's requirements and the shelf life of the drugs.

#### **4.1.7 Storage conditions**

BIBW 2992 tablets must remain in original containers. Tablets are humidity-sensitive; therefore, bottles must be kept tightly closed. BIBW 2992 must be stored at the study site in a limited access area not above 30°C and protected from light.

TMZ should not be stored above 30°C. Tablets are humidity and light sensitive; therefore, tablets should stay in the original bottle and bottles must be kept tightly closed.

## **4.2 CONCOMITANT THERAPY**

### **Concomitant medication**

**Hematopoietic growth factors and/or transfusions are not permitted** during the concomitant chemoradiation phase (unless patients have experienced a DLT or medical emergency for which they are appropriately indicated). Supportive care medications for rash, diarrhoea and nausea/emesis are permitted .

In regimen M:

- PCP prophylaxis is required for all patients receiving concomitant TMZ and RT.
- Anti-emetic prophylaxis is recommended prior to the initial dose of concomitant RT and TMZ
- Anti-emetic prophylaxis is strongly recommended during TMZ maintenance phase

Treatment with certain agents which may interfere with trial medication is prohibited (See section 4.2.2).

All concomitant (non-oncological) therapies starting or changing during the trial are allowed but should be recorded in the patient file and in the eCRF except for vitamins, appetizers or nutrient supplements.

Trade name, indication, dose and dates of administration will be documented. If patients receive parenteral nutrition during the trial, the components are not required to be documented in details. It should just be indicated as “parenteral nutrition” and the form be completed. If a patient requires anesthesia, it will be sufficient to indicate “anesthesia” without specifying the details.

### **Radiotherapy**

The study treatment will be administered with standard radiotherapy. Radiotherapy will be given as fractionated focal irradiation at a dose of 2 Gy per fraction given once daily five days per week (Monday through Friday) over a period of six weeks with a total dose of 60 Gy (see appendix 10.6).

#### **4.2.1 Rescue medication and additional treatment**

Rescue medications to reverse the action of BIBW 2992 or TMZ are not available.

Careful assessment of all patients with an acute onset and/or unexplained worsening of pulmonary symptoms (dyspnoea, cough, fever) should be performed to exclude Interstitial Lung Disease (ILD). Study drugs should be interrupted pending investigation of these symptoms. If interstitial lung disease is diagnosed, study drug must be permanently discontinued and appropriate treatment instituted as necessary.

Patients who present with symptoms of keratitis, such as acute or worsening eye inflammation, lacrimation, light sensitivity, blurred vision, eye pain and/or red eye should be referred promptly to an ophthalmic specialist. If a diagnosis of ulcerative keratitis is confirmed, treatment with BIBW 2992 should be interrupted or discontinued. If keratitis is diagnosed, the benefits and risks of continuing treatment with BIBW 2992 should be carefully considered. BIBW 2992 should be used with caution in patients with a history of keratitis, ulcerative keratitis or severe dry eye. Contact lens use is a risk factor for keratitis and ulceration.

#### **4.2.2 Restrictions**

Additional experimental anti-cancer treatment and/or standard chemo-, immunotherapy, hormone treatment is not allowed concomitantly with the administration of study treatment.

BIBW 2992 is a substrate of the P-gp transporter. Caution should be exercised when combining BIBW 2992 with P-gp modulators. For a list of potent P-gp inhibitors and inducers see Appendix 10.7.

In any patient ongoing in the trial receiving BIBW 2992 and a concomitant potent P-gp inhibitor or inducer at the time of amendment 2 being implemented (26th of April 2010), the decision for continuation of either drug will be based on the individual circumstances of the patient upon discussion with the responsible BI clinical monitor.

#### **4.2.3 Management of expected adverse events**

##### Management of diarrhoea

Close monitoring and proactive management of diarrhoea is essential for successful treatment of patients with BIBW 2992 and/or TMZ. Early and appropriate intervention can prevent the development of more severe diarrhoea. In most cases, loperamide controls diarrhoea caused by BIBW 2992 and/or TMZ.

Loperamide should be available at the start of therapy and kept with the patient at all times; it is therefore advisable that patients be given a prescription at the time of initiating study treatment.

The recommendations for management are as follows:

- If any diarrhoea is experienced (CTCAE Grade 1), two 2 mg loperamide tablets should be taken immediately, followed by one 2 mg tablet with every loose bowel movement, up to a maximum daily dose of 10 tablets (20 mg).
- Patients should be advised to avoid lactose-containing products or any foods known to aggravate diarrhoea.
- Oral hydration is essential regardless of severity; appropriate rehydration (1.5 litres/m^2/day plus equivalent of actual fluid loss) has to be ensured in the event of CTCAE Grade 2 and Grade 3 adverse reaction.
- For CTCAE Grade 3 diarrhoea lasting  $\geq 2$  days or CTCAE Grade 2 diarrhoea lasting  $\geq 5$  days despite adequate antidiarrhoeal treatment, BIBW 2992 and/or TMZ must be paused until recovery to CTCAE  $\leq$  Grade 1 or baseline in the individual treatment course. Upon recovery, BIBW 2992 and/or TMZ should be resumed at a reduced dose according to the dose reduction scheme outlined in Section 4.1.4.

The occurrence of diarrhoea and the outcome of treatment will be recorded in the AE section of the eCRF. Antidiarrhoeal treatments should be documented in the concomitant medication section of the eCRF.

If despite optimal supportive care and the treatment pause, diarrhoea does not resolve to CTCAE Grade  $\leq 1$  or baseline within 14 days, the patient must be removed from the study. Exception to this in patients who derive obvious clinical benefit according to the investigator's judgment could be considered upon discussion with BI's Clinical Monitor Local (CML).

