##### **4.1.4.1.1 Dose escalation scheme for BIBW**

Initially, 3 evaluable patients will be treated per dose level. As soon as one patient experiences a DLT (see section 5.2.3), 3 new patients will be treated at that dose level, to treat a minimum of 6 evaluable patients. If no other patients experience DLT the dose will be escalated to the next level and 3 further patients treated. If two or more of six patients

experience DLT, three additional patients will be treated at one dose tier below unless six have already been treated at that dose tier.

The MTD (see section 5.2.4) is the highest dose at which no more than one of 6 patients experiences DLT. Once the MTD is determined, patient enrolment at higher dose tiers will be suspended.

The MTD cohort in each Regimen may be expanded to include up to 12 patients.

Intra-patient dose escalation will not be permitted.

The first three patients at each dose level will be treated and observed for at least 6 weeks (42 days) during RT before the next cohort of new patients are treated at the next higher dose level (Table 4.1.4.1.1: 2 and 4.1.4.1.1: 3).

Table 4.1.4.1.1: 1 Rules for dose escalation for regimen M and U

Number of Patients with DLT at a Given Dose Level	Escalation Decision Rule
0 out of 3	Enter 3 patients at the next dose level.
1 out of 3	Enter at least 3 more patients at this dose level. - If 0 of these 3 patients experience DLT, proceed to the next dose level. - If 1 or more of this group suffer DLT, then dose escalation is stopped. Three (3) additional patients will be entered at the next lower dose level if only 3 patients were treated previously at that dose.
$\geq 2$ out of 3	Dose escalation will be stopped. Three (3) additional patients will be entered at the next lower dose level if only 3 patients were treated previously at that dose.

The decision regarding dose escalation steps will only be made after agreement with the sponsor's Trial Clinical Monitor (TCM).

Dose escalation and entry of patients into the next dose cohort will begin only after accrual of the required minimum number of patients has been achieved and all patients in the cohort are considered following completion of 6 weeks BIBW2992 treatment ((42 days ) during RT). Patients who are not treated until the end of these 6 weeks for any reasons other than DLT will be replaced (section 6.3.1).

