### 4.1.4.1.2 Dose reduction scheme for BIBW: Regimen U and M

If a patient develops side effect that meets criteria for DLT (for definition refer to Section 5.2.3) regardless of treatment cycle, treatment with BIBW 2992 must be paused. If all drug-related adverse events recover to CTCAE Grade 1 or baseline (whichever is higher) within 14 days of stopping treatment with BIBW 2992, treatment may be resumed with dose reductions according to Table 4.1.4.1.2: 1. Otherwise, the patient will be taken off study. Exceptions to this are patients who derive obvious clinical benefit according to the investigator's judgment. These patients could be considered in agreement with BI's Trial Clinical Monitor (TCM) for further treatment.

If a patient need to dose reduced BIBW 2992 during RT, the dose of BIBW 2992 during the maintenance period will need to be discussed and decided on a case to case base between BI Trial Clinical Monitor and the investigator at site (keep BIBW2992 reduced daily dose or change as planned for 40mg BIBW2992 daily)

Table 4.1.4.1.2: 1 Dose reduction scheme for Regimen M and U

Treatment prior to treatment pause and dose reduction BIBW (mg)	Dose reduction		
	1 st DLT BIBW (mg)	2 nd DLT BIBW (mg)	3 rd DLT
20	Off-study		
30	20	Off-study	
40	30	20	Off-study

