#### Management of nausea and vomiting

Nausea and vomiting may significantly affect patients' adherence to the treatment and their quality of life. In order to reduce the occurrence and the intensity of emesis, the patients should be treated according to the recommendation given in Table 4.2.3: 1.

Table 4.2.3: 1 Management of nausea and vomiting

CTCAE Grade	Antiemetic treatment
Nausea = grade 1 and Vomiting = grade 0	No antiemetic treatment unless judged necessary by investigator
Nausea = grade 2 and Vomiting = grade 0	Antiemetic treatment   Pause BIBW 2992 and/or TMZ treatment if grade 2 vomiting or grade 2 nausea persist for 7 or more consecutive days despite optimal supportive care. Resume treatment when CTCAE grade $\leq 1$ .
Nausea = grade 0, 1 or 2 and Vomiting = grade 1 or 2	Antiemetic treatment 
Vomiting $\geq$ grade 3 or Nausea $\geq$ grade 3	Pause BIBW 2992 and/or TMZ treatment

	until return to CTCAE grade $\leq$ 1 or baseline  .
--	-----------------------------------------------------------------

1 Antiemetic treatment should follow the recommendations given in the Consensus Statement of the Antiemetic Subcommittee of the Multinational Association of Supportive Care in cancer (MASCC): Prevention of chemotherapy- and radiotherapy-induced emesis: Results of the Perugia Consensus Conference (R06-0986).

2 Baseline is defined as the CTCAE grade at the start of treatment.

After a treatment pause the dose of BIBW 2992 should be reduced according to the dose reduction scheme in Table 4.1.4.1.2: 1. The occurrence of nausea and/or vomiting and the outcome of treatment will be recorded in the AE section of the eCRF. Antiemetic treatments should be documented in the concomitant medication section of the eCRF with the start and end of treatment dates and daily dose. In case of nausea and/or vomiting  $\geq$  CTCAE grade 2, appropriate hydration (1.5 L/m^2/day plus hydration deficit) must be ensured.

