#### b) Non-hematologic adverse reaction:

1. CTCAEv3 Grade  $\geq 3$  nausea or vomiting is occurring despite appropriate use of standard anti-emetics for at least three days.
2. CTCAEv3 Grade  $\geq 3$  diarrhoea despite appropriate use of standard anti-diarrheal therapy for at least three days.
3. CTCAEv3 Grade  $\geq 3$  rash despite standard medical management as outlined in Section 4.2.3 and lasting  $>7$  days.
4. CTCAEv3 Grade  $\geq 2$  cardiac left ventricular function.
5. CTCAEv3 Grade  $\geq 2$  worsening of renal function as measured by serum creatinine, newly developed proteinuria, or newly developed decrease in glomerular filtration rate.
6. All other non-hematological toxicities of CTCAEv3 Grade  $\geq 3$

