### **6.3.1 Replacement of patients**

Patients who do not receive study treatment during the chemoradiation phase for more than 5 consecutive days or more than 8 non-consecutive days for any reasons other than DLT will be replaced.

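### The DLT percentage is planned on all treated patients, while the MTD rule counts evaluable patients, so each replaced patient lowers the reported figure

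*Protocol*

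**What the plan says.** **Who counts for the MTD.** Protocol 4.1.4.1.1 starts each dose level with three evaluable patients. After one DLT, "3 new patients will be treated at that dose level, to treat a minimum of 6 evaluable patients". Section 5.2.4 allows at most one patient with DLT among six and restates this as an incidence limit of 17% (1/6).

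**Who is replaced.** Section 4.1.4.1.1 replaces patients who do not complete the six weeks for a reason other than DLT. Section 6.3.1 adds that patients without study treatment in the chemoradiation phase "for more than 5 consecutive days or more than 8 non-consecutive days for any reasons other than DLT will be replaced".

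**How a patient can be off drug without a DLT.** Under protocol 4.2.3, for Grade 2 diarrhoea of at least five "days despite adequate antidiarrhoeal treatment, BIBW 2992 and/or TMZ must be paused until recovery to CTCAE" Grade 1 or baseline. The text continues: "Upon recovery, BIBW 2992 and/or TMZ should be resumed at a reduced dose according to the dose reduction scheme outlined in Section 4.1.4". The nausea and vomiting table also directs a pause "if grade 2 vomiting or grade 2 nausea persist for 7 or more consecutive days despite optimal supportive care", and then: "After a treatment pause the dose of BIBW 2992 should be reduced according to the dose reduction scheme in Table 4.1.4.1.2: 1". The DLT criterion in 5.2.3 is Grade 3 or worse "diarrhoea despite appropriate use of standard anti-diarrheal therapy for at least three days", and Grade 3 is also the floor for nausea and vomiting. Persistent Grade 2 events can therefore lead to a pause and never be DLTs.

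**Who is in the percentage.** Protocol 7.3 includes everyone who received at least one administration in the safety analysis, and 7.3.1 plans the number and percentage with DLT per dosage cohort. SAP 6.3 defines one visible set, the treated set (at least one dose taken), for all analyses. SAP 7 bases percentages on all patients in the set and shows them as whole numbers. SAP 7.4 says the DLT summary is meant to determine the MTD.

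**The concern.** The primary table and the limit it will be read against describe different populations. The limit is a fraction of evaluable patients. The planned percentage keeps replaced patients in the denominator. Replacement happens only for non-DLT reasons, so those patients add nothing to the numerator, and the difference runs one way: the reported DLT percentage can only fall.

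The table is the formal presentation of the primary endpoint. The optional safety analysis in protocol 7.3.4 also has MTD determination among its objectives and leaves its details to the SAP. A reader who compares the cohort percentage with 17% would be using a figure that the MTD rule does not define. In a cohort with several replacements, that figure would suggest a lower DLT rate than the one the escalation decision was based on.

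**Working it through.** **Inputs**
- *e*, evaluable patients: 6 after a first DLT (protocol 4.1.4.1.1); up to 12 if the MTD cohort is expanded (4.1.4.1.1, 7.6).
- *d*, patients with DLT.
- *r*, replaced patients who stay in the treated set. The documents give no rate, so *r* is an assumption, taken from 0 to 6.
- Limit: 17%, i.e. 1/6 (5.2.4).

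**Step 1: the plan's own figures.** 1/6 = 16.7%, which is 17% in whole numbers. The sample size in 7.6 is 2 × (12 + 6 + 6) = 48. Both reproduce.

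**Step 2: formulas.** Evaluable percentage = *d*/*e*. Treated-set percentage = *d*/(*e* + *r*), because a replaced patient adds to the denominator only.

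**Step 3: six evaluable patients.**

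| r | treated | 1 DLT | 2 DLTs |
|---|---|---|---|
| 0 | 6 | 16.7% | 33.3% |
| 1 | 7 | 14.3% | 28.6% |
| 2 | 8 | 12.5% | 25.0% |
| 3 | 9 | 11.1% | 22.2% |
| 4 | 10 | 10.0% | 20.0% |
| 5 | 11 | 9.1% | 18.2% |
| 6 | 12 | 8.3% | 16.7% |

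The row r = 0 is the evaluable figure. A dose that fails with two DLTs in six reads 17% on the treated set only at r = 6.

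**Step 4: expanded cohort, 12 evaluable.** Two DLTs: 2/12 = 16.7%, then 2/13 = 15.4% and 2/14 = 14.3% with one or two replaced. Three DLTs: 3/12 = 25.0%, reaching 3/18 = 16.7% at r = 6.

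**Step 5: how many replacements are plausible.** The protocol allows up to 30 patients per regimen, and 7.6 accounts for 12 + 6 + 6 = 24. That leaves 6 places per regimen. If those places are meant for replacements (an assumption), six in a single cohort would use them all.

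**Step 6: link to the pause rules.** A pause for Grade 2 diarrhoea of six or more consecutive days exceeds the 6.3.1 limit. The patient is replaced and becomes part of *r*. With a pause of five days or fewer, and no more than eight days missed in total, the patient stays evaluable and DLT-free at the assigned dose even if the dose is then reduced. One hypothetical case at 40 mg: Grade 2 diarrhoea on days 8–12, pause on days 13–17, 30 mg from day 18. That gives 12/42 = 29% of days at 40 mg and (12 × 40 + 25 × 30)/(42 × 40) = 1230/1680 = 73% of the planned dose. It shows what the cohort DLT table would not display; it does not estimate how often this happens.

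**The case against.** The strongest reply is that the MTD is decided by a count. Protocol 5.2.4 allows no more than one DLT in six, the 17% only restates 1/6, and SAP 7.4 refers back to 5.2.4. Starting from 1/6, dilution changes no conclusion because the dose already passes. A failing 2/6 cohort still reads 29% or 25% with one or two replacements. This stands and limits the point to reporting.

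A reader might infer more. These stronger readings are not supported:

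- **That the MTD will be biased.** Escalation follows the evaluable count, and the documents give no replacement rate.
- **That an expanded cohort could cross the limit, with 2/12 = 17% treated but 2/11 = 18% or 2/10 = 20% evaluable.** This leaves non-evaluable patients unreplaced, while 4.1.4.1.1 and 6.3.1 say they are replaced. The protocol also states no separate rule for applying 17% to an expanded cohort.
- **That non-DLT reductions go uncounted.** SAP 7.8.1 classes non-serious, non-DLT AEs that lead to reduction or discontinuation as other significant AEs, with their own patient table, and SAP 6.1 presents results by assigned group. The visible gap is narrower: that table names no pauses, leaves out serious AEs and is not limited to the radiotherapy window.
- **That violation code C2.1 would mislabel reductions directed by 4.2.3.** Section 4.1.4.1.2 does open with "If a patient develops side effect that meets criteria for DLT", but 4.2.3 itself sends these patients to that scheme, so a step from 40 to 30 mg follows it. With no per-protocol set, the code would exclude nobody.
- **That no action exists at 20 mg.** The reduction table has a 20 mg row, which takes the patient off study.

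**Conclusion.** The denominator mismatch is real. As the visible plan is written, each replaced patient lowers the reported per-cohort DLT percentage: from 16.7% to 14.3%, 12.5% or 11.1% with one to three replaced when there is one DLT in six evaluable patients, and from 33.3% to 28.6% or 25.0% with one or two replaced when there are two. The count-based escalation decision is normally unaffected, and no direction or size of MTD bias is claimed.

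This rests on three assumptions: the numbers of replaced patients are illustrative; a replaced patient has no DLT in the radiotherapy window; and no evaluable set is defined in blanked SAP text. The SAP contents page shows blanked entries between 6.3 and 6.5, between 7.5 and 7.7, and around section 9, so absence there cannot be confirmed. The missing display of pauses is a matter of table layout. Whether pauses or reductions directed by 4.2.3 should count as DLTs is the sponsor's choice.

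**What to change.** 1. In SAP 6.3, define a DLT-evaluable set from protocol 4.1.4.1.1 and 6.3.1: patients with a DLT in the radiotherapy window, plus patients who completed the window without exceeding the missed-dose limits.
2. In SAP 7.4, use this set as the denominator for the DLT proportion and the MTD statement, by regimen and dose cohort. Show the treated-set figure beside it as a supplement, with the number replaced.
3. Optionally, list by cohort the drug-related afatinib pauses, reductions and discontinuations in the radiotherapy window that were not classed as DLT, including those in replaced patients.

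The cost is one set definition, one extra denominator and, if wanted, one listing from dosing and AE data already collected. The escalation rule does not change. The downside is slightly more tabulation and a possibly higher stated DLT percentage.
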